Open repair of thoracoabdominal aneurysms, especially in patients with preexisting comorbidities, is fraught with complications. A meta-analysis of 7,833 open repairs of thoracoabdominal aneurysm repairs from 2000 to 2010 found a 30 day mortality rate of 7%, in-hospital mortality of 10%, spinal cord ischemia rates of 7.5%, renal failure rates of 19%, and pulmonary dysfunction rates of 36%²¹. Predictors of adverse events after elective open repair based on pre-existing comorbidities have been established. Advanced age (>70 years)²²⁻²⁵, respiratory disease²⁴, renal insufficiency²⁶, coronary artery disease^{22,25}, symptomatic aneurysms, extent 1 and 2 aneurysms²⁷⁻³⁰, and diabetes³¹ are reported to be a predictor of 30-day mortality. Cardiac function³², extent 1 and 2 aneurysms^{28,33-35}, symptomatic cases³⁵, and diabetes³¹ are reported to be predictors of paraplegia. The outcomes reported above are in a low- to moderate- risk patient population. It is a logical extension to assume the outcomes in moderate- to high- risk patients would be worse.

Open Surgical Repair of Ruptured, Urgent, and Emergent TAAAs

Open repair of any thoracoabdominal aneurysms, especially in patients with preexisting comorbidities, is fraught with complications. A recent review of emergent patients with a ruptured TAAA looked at the overall mortality of 51 emergently treated patients with TAAA between 1994 and 2014. The study evaluated Crawford Type I, II, III, and IV presenting hemodynamically unstable (94%) and hemodynamically stable (3%). In this study 54.9% (28/51) had true aneurysms and 45% (23/51) had dissecting aneurysms. These were further broken into 94% (48/51) that presented emergently requiring treatment in 2-6 hours and 6% (3/51) that presented urgently and required treatment within 24 hours. The overall mortality in this study was 43% (23/51); 15% (8/51) of these occurring during the procedure and 27% (14/51) occurred post-operatively. Of the 84% (43/51) that survived the initial procedure, 16% (6/42) developed paraplegia/paraparesis, 18.6% (8/43) had acute renal failure, 35% (15/43) had pulmonary insufficiency, and 18.6% (8/43) with post-operative bleeding. The average visceral ischemic time was 36 minutes and the average blood loss was 2875cc¹⁴.

Open Surgical Repair of Chronic Type B Dissections

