Treatment of TAAA aneurysms in all patients that meet entry criteria will be considered for this study. All patients diagnosed with a TAAA repair are considered high risk due to the natural history of a patient with a TAAA. Their options are limited for endovascular repair and due to the comorbidities in this population they are all high risk open repair. Additionally, all patients undergoing open surgical repair of a thoracoabdominal aneurysm are considered to be at high risk for comorbidities and complications. Based on initial clinical experience, we believe that we can treat all patients with outcomes better to those of open surgical repair with less cost over the year. The current approach is an endovascular repair with lower surgical morbidity and mortality rate compared to open repair. Endovascular repair may also decrease the recovery time and length of hospital stay. From the initial clinical evaluation, certain patients may not be a good candidate for this approach have been identified. This patient population includes patients presenting emergently, with compromised renal access, or dissections. The inclusion and exclusion criteria for this study has been refined to present a patient population that we feel may significantly benefit from this

procedure without undue risk. The inclusion criteria listed in section 6 including aneurysm characteristics, access vessel morphology, minimum neck length, diameter of aneurysm, branch vessel size, patency of the four major visceral vessels, and size of distal fixation site are required as inclusion criteria to achieve an adequate seal zone and optimal placement with the stent graft and branches.

The patient population being excluded from this study includes patients with a ruptured aneurysm (or contained rupture), obstructive stenting of the visceral vessels, or a dissection in the treated portion of the aorta. Also patients with thrombus or excessive calcification within the neck of the aneurysm will be excluded as they put the patient at high risk of aneurysmal rupture or embolic event during surgical manipulation. Anatomy that does not allow for primary or assisted patency of the left subclavian artery will be excluded because it is required for access. Additionally, anatomy that would not allow for maintenance of at least one patent hypogastric artery will be excluded in order to prevent organ and/or pelvic ischemia and paraplegia.

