The outcomes from prior clinical evaluation of the study device, including successfully treating 99% (84/85) of the intended target vessels and 96% (27/28) limb patency observed at one year, demonstrate the potential benefits of the device. When contrasted with open repair's significant complication rates and branch fenestrated device's significant anatomic and logistic limitations, the potential risk of the proposed novel graft does not outweigh the potential benefit of widened anatomic availability and improved patency rates. Given the potential benefits, we feel that it is justified to expose the target patient population to the potential risk. The non-clinical testing performed by Medtronic and the clinical results reported by Sanford Health show adequate safety of the device to support a durable comparison of longitudinal cost and patient centered outcomes for patients treated with the Medtronic Valiant Thoracoabdominal Stent Graft System, and provide a valid comparison of open and endovascular surgical outcomes for TAAA patients.

4. Study Procedures

- a. Study design, including the sequence and timing of study procedures (distinguish research procedures from those that are part of routine care).

Patient Population

The study will evaluate 16 patients with type I, II, III, and V thoracoabdominal aneurysms meeting protocol inclusion criteria. The patient population includes both male and female patients greater than 18 years old with a life expectancy of at least one year.

Study Type and Duration

This study is a prospective, single-center, non-randomized, multi-arm study to evaluate the therapeutic benefit of the Valiant Thoracoabdominal Stent Graft System. A total of 16 patients (10 in the primary study arm; 6 in the expanded selection criteria arm) will be enrolled in the study for treatment with the Valiant Thoracoabdominal Stent Graft System. The duration of the investigation is anticipated as follows:

- Time to Complete Enrollment: 24 months
- Subject Follow-up Time: 5 years from last subject enrollment
- Total Duration Time: 7 years

Intended Use

The Valiant Thoracoabdominal Stent Graft System is indicated for the endovascular treatment of thoracoabdominal aortic aneurysm (Crawford Type 1, 2, 3 and 5) in patients with the following characteristics:

- o An aneurysm with a maximum diameter of > 5.5 cm or 2 times the normal diameter just proximal to the aneurysm using orthogonal (i.e., perpendicular to the centerline) measurements

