N/A

g. Description of what happens to participants receiving therapy when study ends or if a participant's participation in the study ends prematurely.

N/A

5. Inclusion/Exclusion Criteria

Modified Inclusion Criteria

A patient may be entered into the study if the patient has at least one of the following:

- An aneurysm with a maximum diameter of ≥ 5.5 cm or 2 times the normal diameter just proximal to the aneurysm using orthogonal (i.e., perpendicular to the centerline) measurements
- Aneurysm with a history of growth ≥ 0.5 cm in 6 months
- Saccular aneurysm deemed at significant risk for rupture
- Symptomatic aneurysm greater than or equal to 4.5 cm
- Axillary or brachial and iliac or femoral access vessel morphology that is compatible with vascular access techniques, devices or accessories, with or without use of a surgical conduit
- Proximal landing zone for the thoracic bifurcation stent graft that has:
 - ≥ 2.5 cm of healthy/nondiseased tissue (including previously placed graft material) (neck) distal to the left subclavian artery (LSA) and a diameter in the range of 26-42 mm
 - Adequate distance from the celiac artery, in order to accommodate cannulation from the antegrade access point when considering the total deployed length of the thoracic bifurcation and visceral manifold
- Minimum branch vessel diameter greater than 5 mm
- Iliac artery distal fixation site, including both native tissue and previously placed graft, greater than or equal to 15 mm in length and diameter in the range of 8 – 25 mm
- Age: ≥ 18 years old
- Life expectancy: > 1 year

Exclusion Criteria

General exclusion

- Patient is a good candidate for and elects open surgical repair
- Can be treated in accordance with the instructions for use with a legally marketed endovascular prosthesis
- Is eligible for enrollment in a manufacturer-sponsored IDE at the investigational site
- Unwilling to comply with the follow-up schedule
- Inability or refusal to give informed consent by patient or legal representative
- Patient is pregnant or breastfeeding
- Patient has a contained rupture
- Patient has a ruptured aneurysm
- Patient has a dissection in the portion of the aorta intended to be treated
- Obstructive stenting of any or all of the visceral vessels
- Poor performance status including two major system failures (including but not limited to cardiovascular, pulmonary, renal, hepatobiliary, and neuromuscular)

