The primary technical safety endpoint is freedom from major adverse events (MAE) at 30 days or during hospitalization if this exceeds 30 days. Major adverse events include all-cause mortality within 30 days of the procedure, bowel ischemia, myocardial infarction, paraplegia, renal failure, respiratory failure, and stroke.

The primary effectiveness endpoint is the proportion of study subjects with treatment success at 1 year. Treatment success is defined as a composite of technical success and freedom from the following:

- Aneurysm enlargement i.e., ≥ 5 mm as compared to any previous CT measure using orthogonal (i.e., perpendicular to the centerline) measurements
- Aneurysm rupture
- Aneurysm-related mortality
- Conversion to open repair
- Secondary intervention for migration, Type I and III endoleaks, device integrity failure (e.g., fracture), and patency-related events (i.e., device component stenosis or occlusion and embolic events)

The primary non-technical endpoint is improvement in quality-of-life scores (by SF36) and reduced 1 year costs for patients who undergo endovascular repair vs open surgery.

B. Secondary outcome variables.

Secondary endpoints include:

- Technical success and the individual components of technical success:

- Successful delivery
- Deployment at the intended implantation site
- Patency of all endovascular graft and stent components
- Absence of device deformations requiring unplanned placement of an additional device
- Absence of inadvertent covering of aortic branch vessels
- Successful withdrawal
- Freedom from the individual components of the primary safety endpoint at 30 days.
 - Death
 - Bowel ischemia
 - Myocardial infarction
 - Paraplegia
 - Renal failure
 - Respiratory failure
 - Stroke
- Freedom from paraparesis at 30 days
- Treatment success and freedom from the following at each follow-up interval:
 - Aneurysm enlargement
 - Aneurysm-related mortality
 - Aneurysm rupture
 - Conversion to open repair
 - Secondary intervention for:
 - Migration
 - Type I endoleak
 - Type III endoleak
 - Device integrity failure (e.g., fracture)
 - Patency-related events (i.e., device stenosis or occlusion and embolic events)
 - Renal failure
 - All-cause mortality
 - Endoleaks
 - Device integrity failure (e.g., fracture)
 - Patency –related events (i.e., endovascular graft or stent component stenosis or occlusion and embolic events)
 - Other device-related events

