C. Statistical plan including sample size justification and interim data analysis.

Sample Size Justification

The sample size for the study is limited to 16 patients (10 subjects in the primary study arm and 6 subjects in the expanded selection criteria arm), as this is adequate to provide preliminary clinical safety data and effectiveness of the device and provide the comparator group for open thoracoabdominal surgery patients. The device, while novel, has been evaluated in a clinical setting and has initially demonstrated both safety and effectiveness. The limited sample size allows adequate patient data to be collected under a controlled protocol without exposing a large patient population to the risk associated with a novel device design. The safety and effectiveness data collected in this study will be pooled with other physician sponsored investigational device exemptions (PS-IDEs) evaluating the Visceral Manifold System and should be sufficient to develop an appropriate pivotal study.

In reference to the objective of cost of TAAA delivery, prior studies suggest the one-year costs associated with open TAA repairs are approximately \$150,000+/- \$10,000.⁵⁶ Assuming a power of 80% and $\alpha=0.05$, we would need 20 patients per group to detect a difference of \$20,000 between the mean one-year costs of open TAA repair vs TEVAR. Longitudinal costs over a one year period, inclusive of global healthcare costs (readmission, outpatient care, rehabilitation stays) are not available from the literature, but would be analyzed in this study, and thus inform healthcare policy, reimbursement strategies, and hospital administrators.

Data Presentation and Analysis Plan

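### The one-year cost and SF-36 comparison with open surgery is confounded by indication: treatment follows open candidacy and patient choice, and the plan sets no common eligibility or adjustment

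*Combined protocol and SAP*

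**What the plan says.** Section 4 (Study Type and Duration) states: "This study is a prospective, single-center, non-randomized, multi-arm study". The arms are both device arms: "A total of 16 patients (10 in the primary study arm; 6 in the expanded selection criteria arm) will be enrolled". Section 5 (General exclusion) removes a patient who meets this description: "Patient is a good candidate for and elects open surgical repair".

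Sections 2 and 7.A make SF-36 improvement and "reduced 1 year costs for patients who undergo endovascular repair vs open surgery" the primary non-technical endpoint. Section 7.C (Sample Size Justification) says the 16 device patients will "provide the comparator group for open thoracoabdominal surgery patients". The synopsis that closes Section 3 says existing data support a durable comparison of longitudinal cost and patient-centered outcomes, and that they "provide a valid comparison of open and endovascular surgical outcomes for TAAA patients".

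On risk, Section 3 (Justification for Specific Patient Selection Criteria) says of the device population that "due to the comorbidities in this population they are all high risk open repair". Under Open Surgical Repair it says of published series: "The outcomes reported above are in a low- to moderate- risk patient population". Section 6 adds that comorbidity rules out open repair for many of these patients.

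**The concern.** The protocol itself supplies both links needed for confounding by indication. Fitness for open surgery affects which treatment a patient receives (Sections 5 and 6). Risk also affects outcome: Section 3 infers worse open results in higher-risk patients. One-year cost is exposed in the same way, because Section 3 expects the open-versus-endovascular difference to arise largely after discharge, in subacute and rehabilitation care. That use plausibly depends on baseline health as well as on the operation.

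Nothing in the plan offsets this. The open group has no stated source, period, eligibility, number, matching or adjustment. Risk adjustment appears only in the Abstract, as something the study may help to develop. The limitations listed in Section 7 are a single center and a small population.

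The sponsor sees the problem elsewhere. Section 3 keeps emergent, urgent and ruptured cases out of the primary arm because they could confound the safety and effectiveness results. The comparison with open surgery has no equivalent safeguard. At stake is whether the study may report that the device reduces cost or improves quality of life.

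**Working it through.** **1. The plan's own cost figure.** Section 7.C gives a mean of $150,000 +/- $10,000, a difference of $20,000, 80% power, alpha 0.05 and 20 per group. Reading +/- as a standard deviation (SD) and taking a two-sided test:

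n per group = 2 x (1.96 + 0.84)^2 x (10,000/20,000)^2 = 3.9, so 4. An exact t-test needs 6 (power 87.6%; 5 per group gives 79.1%).

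The stated 20 is not reproduced. It needs an SD of about $22,000 (t-test) to $22,600 (normal approximation). That mismatch is a separate matter, but it means both SDs should be carried below.

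**2. What the comparison estimates.** Let S be the true saving from the device. Let g be the case-mix gap: the open group's expected cost minus the device group's, if both had the same procedure. Then

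expected (open mean - device mean) = S + g.

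A lower-risk open group gives g < 0, and a sicker one gives g > 0. Sample size does not enter the formula, so more patients would not remove g.

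**3. Which sign?** The passages point both ways.

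| Pointing to a lower-risk open group | Pointing the other way or neutral |
|---|---|
| Fit patients who choose open repair leave the device group (Section 5) | Fit patients who decline open repair may still enter it (Section 5) |
| Many TAAA patients cannot have open repair (Section 6) | Section 3 also calls all open-repair patients high risk |
| The expanded arm admits rupture, emergent cases, creatinine >= 2.0 mg/dL and two-system failure | The primary arm excludes rupture, treated-segment dissection, creatinine >= 2.0 mg/dL and two-system failure; the open group has no such limits |

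**4. Size, as an assumption.** No document figure measures g. Take -$15,000 to +$15,000, which is 10% of $150,000 either way. At the limits, 15,000/20,000 = 75% of the design difference.

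The standard error for 16 device patients against an assumed 20 open patients is SD x sqrt(1/16 + 1/20): $3,354 at SD $10,000 and $7,379 at SD $22,000. Two-sided t-test, alpha 0.05; each cell shows SD $10,000 / SD $22,000:

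| g | Chance of finding a true $20,000 saving | Chance of a significant result when S = 0 |
|---|---|---|
| -$15,000 | 30% / 10% | 99% / 51% (device looks dearer) |
| -$10,000 | 83% / 26% | 83% / 26% (device looks dearer) |
| $0 | >99.9% / 75% | 5% / 5% |
| +$10,000 | >99.9% / 98% | 83% / 26% (device looks cheaper) |
| +$15,000 | >99.9% / >99% | 99% / 51% (device looks cheaper) |

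**5. Role of the expanded arm.** It supplies 6/16 = 37.5% of the device patients. If only those six cost more, g is 6/16 of their excess. A gap of $15,000 would then need an average excess of 15,000/0.375 = $40,000 each. Of the 11 listed entry routes to that arm, five are anatomical or concern prior repair or stenting, so 37.5% is not the share of sicker patients.

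**The case against.** A reader might infer that the exclusion rule makes any open comparator lower-risk by design, so that the bias must hide a true saving. The documents do not support that.

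- The rule needs both candidacy and election. A patient who elects open repair would not receive the device in any case, so the rule adds little to ordinary non-random treatment choice.
- The low- to moderate-risk remark in Section 3 describes published series. The Abstract places the cost comparison in the sponsor's own hospital.
- An open series without limits could be sicker than the 10 primary-arm patients, and the bias would then favour the device.
- If the open group were lower-risk, an observed saving would be conservative.

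Two points of wording also stand. In the synopsis, *valid* attaches to surgical outcomes and *durable* to cost and patient-centered outcomes. Section 7.C calls the data preliminary, makes safety the primary purpose, specifies no comparative cost test, and says the data will be separated into the two arms.

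These points leave the direction open, but they do not remove the confounding. Sections 2 and 7.A still word a primary endpoint as a contrast with open surgery, and the arm separation does not say which arm is compared with open patients.

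**Conclusion.** The concern holds as confounding by indication of uncertain direction. Treatment depends on candidacy and preference, the endpoint is comparative, and the plan has no means of making the groups comparable. A lower-risk open group is the more likely case if it is concurrent, especially against the expanded arm, but the design does not guarantee it.

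The size is unknown. The $15,000 limits are an assumption, as are the 20 open patients and the SDs. Within those limits the bias could be up to 75% of the $20,000 sought, enough either to mask a real saving or to produce an apparent one. For scale, the hospitalization costs quoted in Section 3 differ by only 64,531 - 61,909 = $2,622. This should be changed because it governs what the study may conclude on cost and quality of life. The single-arm safety and effectiveness endpoints are not affected.

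**What to change.** 1. In Sections 2, 7.A and 7.C (Data Presentation and Analysis Plan), state that open-versus-device cost and SF-36 figures are descriptive and do not show that the device reduces cost or improves quality of life.
2. In the synopsis at the end of Section 3, remove *durable* and *valid* as descriptions of the comparison.
3. Compare only the 10 primary-arm patients with open patients who meet the same primary-arm medical criteria: unruptured, no dissection in the treated segment, creatinine below 2.0 mg/dL, no two-system failure. Name the source and period of the open cohort so that the filter can be applied.
4. Report the expanded arm separately.
5. Show baseline risk side by side, for example age, creatinine, COPD and Crawford type.
6. State that confounding by surgical candidacy and preference remains after the filter.

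This costs wording, a selection filter and one table. The comparison becomes smaller: with 10 against an assumed 20 open patients at SD $22,000, the standard error rises from $7,379 to $8,521, and power for a $20,000 difference without bias falls from 75% to 62%. The filter may shrink the open group further. The claim is also weaker, which is all that the design can support.
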